As of today no other compassionate use cases for the use of Reparixin in patients with Covid-19 pneumonia have been activated at the San Raffaele Hospital or in other sites.

## **3 OBJECTIVES AND ENDPOINTS**

- Phase 2 Study Objectives: efficacy and safety of of Reparixin treatment as compared to the control arm in adult patients with severe COVID-19 pneumonia

- Phase 3 Study Objectives: efficacy and safety of Reparixin treatment as compared to the control arm in adult patients with moderate or severe COVID-19 pneumonia

### - Phase 2/3 Study Endpoints:

- **Primary Endpoint for Phase 2:** Composite endpoint of clinical events (the patient requires at least one of the following: supplemental oxygen requirement, mechanical ventilation use, admission to ICU, and use of a rescue medication for any reason)
- **Primary Endpoint for Phase 3:** Composite endpoint of death and clinical severe events (the patient dies or requires mechanical ventilation use and/or admission to ICU)
- Secondary Endpoints:
  - Changes in clinical severity score (as recommended by WHO for COVID studies), defined as the time to clinical improvement of two points from the time of randomization on a seven-category ordinal scale or live discharge from the hospital, whichever comes first. The seven-category ordinal scale consists of the following: 1) not hospitalized, with resumption of normal activities; 2) not hospitalized, but unable to resume normal activities; 3) hospitalized, not requiring supplemental oxygen; 4) hospitalized, requiring supplemental oxygen; 5) hospitalized, requiring high-flow oxygen therapy, noninvasive mechanical ventilation, or both; 6) hospitalized, requiring ECMO, invasive mechanical ventilation, or both; and 7) death.
  - Dyspnea severity (Liker scale and VAS scale)
  - Changes in body temperature
  - Changes hematology test values
  - o Duration and quantity of supplemental oxygen treatment
  - Incidence and duration of mechanical ventilation use
  - o Incidence of intensive care unit (ICU) admission need
  - Lung damage extension changes from baseline (assessed by Chest CT or Rx)
  - Change from baseline in lung exudation degree (assessed by Chest CT or Rx)
  - o PaO2
  - o SpO2
  - Partial arterioral oxygen pressure (PaO2) to fraction of inspiration O2 (FiO2) ratio
  - o CRP
  - o Hs-CRP

#### - Exploratory Endpoints (not mandatory):

- Cytokine profile
- o Concentration of Reparixin in serum over time
- o SARS-CoV-2 virologic counts

#### - Safety Endpoints:

- Serious adverse events
- Adverse events (AEs) coded by System Organ Class (SOC) and preferred Term (PT), using the Medical Dictionary for Regulatory Activities (MedDRA).
- The number and percentage of patients with any AE and the number of TEAEs, tabulated by SOC and PT, seriousness, relationship to treatment and severity.

### 4 STUDY DESIGN AND METHODOLOGY

#### 4.1 Phase 2 Study design

The study is designed for the investigational use of a CXCR1 and CXCR2 allosteric antagonist named Reparixin. It will involve 48 adult patients with severe COVID-19 pneumonia in accord with any of the following:

1. Age 18 to 90.

2. Confirmed COVID-19 diagnosis

3. At least one of the following: (1) Respiratory distress,  $RR \ge 30$  breaths/min without oxygen; (2) Partial arterial oxygen pressure (PaO2) / Fraction of inspiration O2 (FiO2) >100 <300mmHg (1mmHg = 0.133kPa).

4. Chest imaging confirms lung involvement and inflammation.

5. Inflammatory status as documented by at least one of the following: Lactate dehydrogenase (LDH) > normal range, C-reactive protein (CRP)  $\geq$  100mg/L or IL-6  $\geq$  40pg/mL, serum ferritin  $\geq$  900ng/mL, XDP >20mcg/mL.

Patients randomized to the active treatment will receive an oral dose of reparixin (1200 mg tablets TID) for 7 days. In case of improvement, treatment can be prolonged at discretion of the investigator up to a total of 21 days of treatment. Patients randomized to the both arms will be offered, in case of worsening (e.g. need of ICU and/or mechanical ventilation), a rescue medication based on their physicians' judgement, without any constrain from the sponsor.

#### 4.2 Phase 3 Study design

In the phase 3 segment of this study, it is planned that patients will be randomized 2:1 to Reparixin or standard of care. Patients randomized to the control arm will be offered a rescue medication with the active treatment (Reparixin 1200 mg oral tablets TID) or Reparixin 2.772 mg/kg body weight/hour IV infusion, if the oral route is unfeasible for the clinical condition. The Phase 3 design will be reassessed and pending re-evaluation based on Phase 2 study results.

**Phase 2 Study Design and Methodology:** Randomized 2:1, controlled, multicentre clinical trial in 48 adult patients with severe COVID-19 pneumonia

**Phase 3 Study Design and Methodology:** Randomized 2:1, controlled, multicentre clinical trial in 111 adult patients with severe COVID-19 pneumonia, to be re-assessed based on Phase 2 results.

# **5 POPULATION**

#### 5.1 Number of patients

A maximum of 48 patients with moderate-to-severe COVID-19 pneumonia will be enrolled in the Phase 2 study. Enrollment can be interrupted at any given time for futility or clear superiority reasons of the oral tablet vs IV infusion, or both vs standard of care, to proceed into Phase 3 or interrupt the clinical study.

The estimated number of 111 patients to be enrolled until the end of Phase 3 will be re-estimated based on the Phase 2 results.

#### 5.2 Inclusion/exclusion criteria

#### Phase 2 Inclusion Criteria:

- 1. Age 18 to 90.
- 2. Confirmed COVID-19 diagnosis
- At least one of the following: ① Respiratory distress, RR ≥ 30 breaths/min without oxygen; ② Partial arterial oxygen pressure (PaO2) / Fraction of inspiration O2 (FiO2) >100 <300mmHg (1mmHg = 0.133kPa).

- 4. Chest imaging confirms lung involvement and inflammation.
- Inflammatory status as documented by at least one of the following: Lactate dehydrogenase (LDH) > normal range, C-reactive protein (CRP) ≥ 100mg/L or IL-6 ≥ 40pg/mL, serum ferritin ≥ 900ng/mL, XDP >20mcg/mL.

Phase 3 Inclusion Criteria: same as above; other criteria TBD based on Phase 2 outcomes.

## Phase 2/3 Exclusion Criteria:

- 1. Cannot obtain informed consent.
- Severe hepatic dysfunction (Child Pugh score ≥ C, or AST> 5 times the upper limit); Severe renal dysfunction (estimated glomerular filtration rate ≤ 30mL / min / 1.73 m2) or receive continuous renal replacement therapy, hemodialysis, or peritoneal dialysis. Serum albumin <2.5 g/dL.

- 3. Patients with hypersensitivity to ibuprofen or to more than one non steroidal anti-inflammatory drug or to more than one medication belonging to the class of sulfonamides (e.g. sulfamethazine, sulfamethoxazole, sulfasalazine, nimesulide or celecoxib; hypersensitivity to sulphanilamide antibiotics alone, e.g. sulfamethoxazole, does not qualify for exclusion)
- 4. Severe, active bleeding such as hemoptysis, gastrointestinal bleeding, central nervous system bleeding, and nosebleeds within 1 month before enrollment.
- 5. Pregnant and lactating women and those planning to get pregnant.
- 6. Participated in other interventional clinical trials with investigational medicinal products, not considered suitable for this study by the researchers.
- 7. At the time of enrollment, patients not in a clinical condition compatible with the oral administration of the study drug.

#### **6** INTERVENTIONS

#### **6.1 Interventional treatments**

#### Phase 2 Investigational treatment

Reparixin in oral pharmaceutical form (1200 mg tablets TID), as follows: **GROUP 1:** Reparixin oral tablets 1200 mg TID for 7 days.

- In case of improvement, treatment can be prolonged at discretion of the investigator up to a - maximum of 21 days of treatment in total.

#### Phase 3 Investigational treatment

Reparixin in oral pharmaceutical form (1200 mg tablets TID). Treatment duration to be decided based on Phase 2 study results.

#### 6.2 Control treatment

#### Phase 2/3 Control treatment

Control group in both the phase 2 and 3 segments will be standard of care, which due to the nature of the COVID-19 pandemic is expected to evolve over time and, thus, cannot be prespecified. This group will be populated in a prospective manner and offered a rescue medication in case of worsening (e.g. need of ICU and/or mechanical ventilation). Due to the evolving understanding of novel treatments being currently tested during the COVID-19 pandemic, the Sponsor will not put any restriction on the selection of the rescue medication during phase 2. In the phase 3, Reparixin will be offered as rescue medication, as oral tablets or as IV infusion in case of unfeasibility of the oral administration due to the clinical conditions (e.g. intubated patients in the ICU).

## 6.3 Preparation, Handling, Storage and Accountability of the study drug

#### Study Drug (REPARIXIN tablets)

## FORMULATION

The investigational product is in the form of oral immediate release 600 mg tablets containing the active ingredient reparixin. Reparixin 600 mg immediate release tablets are white oblong tablets.

NAMES OF INGREDIENTS	AMOUNT PER TABLET	FUNCTION OF INGREDIENT	R EFERENCE TO QUALITY STANDARDS
Reparixin (DF 1681Y)	600.0 mg	Drug substance	Internal monograph
Cellulose Microcrystalline	141.48 mg	Diluent/ Disintegrant	Eur. Ph.
Lactose monohydrate	94.77 mg	Diluent	Eur. Ph.
Croscaramellose Sodium	36.00 mg	Disintegrant	Eur. Ph.
Hydroxypropyl cellulose	20.07 mg	Binder	Eur. Ph.

Refer to the following table for Reparixin tablets Description and Composition.

Silica, colloidal anhydrous	3.15 mg	Glidant	Eur. Ph.
Magnesium stearate	4.50 mg	Lubricant	Eur. Ph.
Total	900 mg	-	-

#### Manufacturing, Packaging and Labelling of Investigational Product

Reparixin tablets will be packaged in white PVDC/PE/PVC/Aluminum blister packages and should be stored at temperatures not higher than 30°C.

The drug is manufactured by Monteresearch according to current Good Manufacturing Practice requirements.

Medication labels will comply with the Competent Authority requirements and will be printed in a Multilanguage format where needed. Refer to the Appendix 4 for reparixin packaging and labeling details.

Reparixin tablets are packaged in white PVDC/PE//PVC/Aluminum blisters in the form of patient kits, numbered to maintain blinding and should be stored at temperature not higher than 30°C.

The Investigator (or pharmacist in those countries where it is required that shipment is made directly to the hospital pharmacy) is responsible for receipt, proper storage and usage of study drug. Partially used or unused study drug boxes should be destroyed on site (and documentation of destruction provided to Dompé farmaceutici s.p.a.) or returned to Dompé farmaceutici s.p.a., at the end of the study. The Investigator, who will keep a cumulative inventory and dispensing records, will maintain all supplies under adequate security. Adequate record of receipt, use or loss of drug will be retained.

Pharmacists will be provided with the 'Instructions to the Pharmacy'.

#### **Dose and Route of Administration**

Oral tablets: For patients able to comply with the oral treatment, it is recommended to take for each administration two Reparixin 600 mg tablets, for the total of three daily administrations. It is advisable to take the tablets with a glass of water to facilitate swallowing. For patients who are unwilling or unable, in the opinion of the investigator, to comply with the oral tablets treatment, is possible to administration, disperse two Reparixin 600 mg tablets in 25 mL of drinking water in a suitable container (e.g. conical tubes for 50 mL Falcon centrifuge). Disgregate the tablets (shaking manually or with the aid of a planetary shaker or a rocker) until obtaining a homogeneous milky suspension (time required 7 - 10 minutes). Keep the prepared suspension at room temperature and protected from light for up to 24 hours. Immediately before administration, manually shake the suspension again until complete and homogeneous resuspension, withdraw using a 50 mL needle-free syringe and administer to the patient using a naso-gastric tube.

## Study Drug (REPARIXIN iv)

# FORMULATION

The investigational product is in the form of concentrate for solution for i.v. infusion packaged into 250 mL clear Glass Vials with the following composition per single (250 mL) unit.

NAME OF INGREDIENT	PER-UNIT FORMULA	FUNCTION OF INGREDIENT	R EFERENCE TO QUALITY STANDARDS
Reparixin (DF1681Y)	8.25 g	Drug substance	Internal monograph
Sodium Dihydrogen Phosphate Dihydrate	1.96 g	Buffer	Eur. Ph.
L-lysine monohydrate	4.78 g	Solubilizer	German Pharmacopoeia - current edition
Sodium hydroxide	qs to pH 8.0	Buffer	Eur. Ph.
Water for injections	qs to 250 mL	Solvent	Eur. Ph.

Refer to the following table for Reparixin i.v. 33mg/mL Description and Composition

## Manufacturing, Packaging and Labelling of Investigational Product

Reparixin will be manufactured by Patheon (Italy) according to current Good Manufacturing Practice requirements.

The Reparixin iv is packaged into 250 mL clear Glass Vials.

The Investigational Product must be kept at a temperature not exceeding 30°C and must not be frozen

Medication labels will comply with the Competent Authority requirements and will be printed in a Multilanguage format where needed. Refer to the Appendix 4 for reparixin packaging and labeling details.

The Investigator (or pharmacist in those countries where it is required that shipment is made directly to the hospital pharmacy) is responsible for receipt, proper storage and usage of study drug. Partially used or unused study drug boxes should be destroyed on site (and documentation of destruction provided to Dompé farmaceutici s.p.a.) or returned to Dompé farmaceutici s.p.a., at the end of the study. The Investigator, who will keep a cumulative inventory and dispensing records, will maintain all supplies under adequate security. Adequate record of receipt, use or loss of drug will be retained.

Pharmacists will be provided with the 'Instructions to the Pharmacy'.

#### **Dose and Route of Administration**

**IV infusion:** In the Phase 3, for patients randomized to the control arm who have worsened after 24hrs and within 14 days from randomization, Reparixin will be offered as rescue medication also as a continuous i.v. infusion into a central vein or dedicated peripherally inserted central catheter at a dose of 2.772 mg/kg body weight/hour for up to 7 days (120hrs).

The Reparixin solution for IV infusion will be provided by the Sponsor.

The dosing solution for infusion will be prepared at the designated Pharmacy or authorized location within each centre according to local guidelines for sterile re-consitution of i.v. injectable solutions. For each 750 mL dosing solution volume, the content of a Vial (250 mL) will be diluted with 500 mL of 0.9% sterile saline to dispense reparixin as 11.00 mg/mL solution. The dosing solution will be placed in a 1000 mL sterile empty Infusion Bag. Dosing solutions will be prepared and used within 72 hours from preparation, unless the site has more restrictive rules

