### **10.1.4 SAFETY DATA**

A total of 448 subjects have been exposed to reparixin in the clinical studies completed to date, of whom 337 and 112 received i.v. formulation and oral tablets, respectively. The patient population exposed to i.v. formulation includes 103 adult healthy subjects (100M/3F), 17 patients with different grades of renal impairment (12M/5F), 16 patients undergoing cardiopulmonary by pass (10M/6F), 46 patients undergoing lung transplantation (23M/23F), 48 patients undergoing kidney transplant (31M/17F), 22 undergoing liver transplant (18M/4F) and 85 receiving intrahepatic pancreatic islet infusion (32M/53F), with 22 patients in this group receiving reparixin twice. Exposure included short or prolonged i.v. infusion up to 10.6 mg/kg over 30min or 133 mg/kg over 48h and, in pancreatic islet and liver transplantation studies, 2.772 mg/kg body weight/hour i.v. continuous infusion for 7 days. Overall, reparixin was safe and well tolerated in both healthy subjects and critically ill patients. In phase 1 studies, no deaths, Serious Adverse Events (SAEs) or Adverse Event (AE)-related withdrawals were reported. The majority of AEs reported were of mild intensity. All subjects had recovered completely or had ongoing adverse events of mild intensity when they were discharged. The safety of reparixin was confirmed also in patients with different grades of renal impairment. In the interaction study no safety concerns were raised during co-administration of midazolam/tolbutamide with reparixin. During phase 2 and 3 studies, AE and SAE profile was similar for both placebo and reparixin groups and no particular safety concerns were raised. Data obtained in the trials in islet transplantation further support the safety profile of the proposed dose, even after a 7 day administration, repeated twice in several patients. Most frequent ADRs were nausea, headache, and vomiting; great majority of these were mild to moderate in nature and none required discontinuation of the Investigational Product. Tachycardia occurred in one patient from Days 5 to 38 after 1st islet infusion was judjed probable in relation to Investigational Product. Vomiting, nausea and headache on Day 5 and 6 after 2nd islet infusion in one patient and erythema, nausea and headache on Days 2 to 6 after 1st islet infusion in another patient were judged highly probable in relation to the Investigational Product. Nausea, vomiting and severe gastrointestinal bleeding associated with anaemia developed in a female patient early after the beginning of reparixin infusion because the patient received a dose of reparixin 3 times as high as that foreseen in the protocol (medical error). These events were assessed as serious by the investigator and by the Sponsor.

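### Protocol section 6.3 limits the Phase 3 intravenous rescue infusion to both 7 days and 120 hours, which differ by 48 hours; the two figures must be reconciled.

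*Protocol*

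**What the plan says.** The instruction is in Protocol section 6.3, under the dose and route of administration for the intravenous product. It applies "In the Phase 3, for patients randomized to the control arm who have worsened after 24hrs and within 14 days from randomization". For them, "Reparixin will be offered as rescue medication also as a continuous i.v. infusion into a central vein" or a dedicated peripherally inserted central catheter, and the rate and limit read "at a dose of 2.772 mg/kg body weight/hour for up to 7 days (120hrs").

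The same rescue is described in the protocol summary (section 1), in sections 4.2 and 6.2, and in SAP section 3. Those places give the rate or the route, and none gives a maximum duration. Section 6.3 is therefore the only place where the limit is set, and it sets two.

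Section 10.1.4 describes exposure in earlier islet and liver transplantation studies as "2.772 mg/kg body weight/hour i.v. continuous infusion for 7 days", without an hour equivalent.

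**The concern.** A limit on total exposure to an investigational drug should have one value. Here two sites could each follow the sentence as written and stop the infusion 48 hours apart. The recipients are control patients who have worsened; section 6.2 gives intubated patients in the ICU as the example.

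Two other parts of the plan would not catch the difference:

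- **Overdose definition (Protocol section 7.3.10).** For the intravenous form it is expressed relative to the daily dose. Running at the correct rate beyond one of the two limits does not change the daily dose.
- **Protocol deviations (SAP sections 4.2.5 and 5.2).** These are judged case by case at the Data Review Meeting, and major ones remove a patient from the Per Protocol set used in the Phase 3 sensitivity analysis. From the current text, the meeting could not decide whether infusion between hours 120 and 168 is within protocol.

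**Working it through.** **Inputs**

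- Rate: 2.772 mg/kg/h (Protocol section 6.3).
- Mode: continuous (section 6.3). No daily pause is described, and section 8.2 rules out temporary discontinuation of study medication. Hours are therefore days × 24.
- Limit in days: 7. Limit in hours: 120 (both section 6.3).

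**Step 1. Try to reproduce the plan's hour figure**

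- 7 × 24 = 168 h, not 120 h.
- In reverse, 120 / 24 = 5 days, not 7.

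The stated 120 h is not reproduced from 7 days, and no schedule in the section makes the two agree.

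**Step 2. Maximum cumulative dose = rate × hours**

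| Limit followed | Hours | Maximum dose |
|---|---|---|
| 7 days | 168 | 2.772 × 168 = 465.70 mg/kg |
| 120 hours | 120 | 2.772 × 120 = 332.64 mg/kg |
| Difference | 48 | 465.70 − 332.64 = 133.06 mg/kg |

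**Step 3. Relative size**

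- 168 / 120 = 1.40, so the longer limit is 40% above the shorter.
- 1 − 120 / 168 = 0.286, so the shorter limit is 28.6% below the longer.

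The absolute gap of 48 h does not depend on the choice of base.

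**Step 4. Check of the method**

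Section 10.1.4 reports earlier exposure of "133 mg/kg over 48h". Rate × clock hours gives 2.772 × 48 = 133.06, which agrees. If that figure included the loading dose described for the lung transplant study in section 2.2, the total would be 4.488 × 0.5 + 2.772 × 47.5 = 133.9. Either way the protocol counts clock hours. That this equals the gap in Step 2 only reflects that both are 48 h at the same rate.

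**Step 5. Illustration for supply**

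A vial holds 8.25 g (section 6.3). Body weight is an assumption, because the documents give none.

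- 70 kg: 332.64 × 70 / 8250 = 2.82 vials, against 465.70 × 70 / 8250 = 3.95.
- 80 kg: 332.64 × 80 / 8250 = 3.23 vials, against 465.70 × 80 / 8250 = 4.52.

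**The case against.** The strongest answer is that no patient can be exposed to this instruction yet. Intravenous reparixin is for Phase 3 only; Phase 2 uses tablets, with rescue left to the physician. The protocol says repeatedly that the Phase 3 design will be reassessed. SAP section 4.7 also requires the final Phase 3 segment to go to the competent authority, as a protocol amendment, before the study proceeds. A reader might infer a present hazard from the section 6.3 wording, and the documents do not support that.

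This stands as a point about timing. It does not remove the contradiction. Section 6.1 marks the duration of the Phase 3 oral treatment as still to be decided, but section 6.3 does not mark its intravenous limit as provisional. SAP section 4.5 speaks of adapting Phase 3 only if needed, so an amendment could leave this parenthesis untouched.

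It is also fair to say that the affected group is narrow: control patients in Phase 3 who worsen within the stated window, for whom the oral route is unfeasible, and whose infusion would run past 120 hours. The wording sets a ceiling, so 133 mg/kg is the largest possible difference and not an expected one.

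**Conclusion.** The inconsistency is real and needs correcting. Section 6.3 gives two maximum durations, 168 h and 120 h, for one continuous infusion. They differ by 48 h and 133 mg/kg, and nothing else in the documents resolves them. The result rests only on unit conversion, the stated rate and the infusion being continuous.

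Four wider inferences are not supported:

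- **That the trial's inference is affected.** The Phase 2 oral regimen, the sample size and the primary analyses do not use the infusion limit. The Phase 3 endpoint is time to first severe event. The protocol's own examples of worsening, need of ICU or mechanical ventilation, are the kinds of event that the endpoint counts, so rescue would usually begin at or after the event.
- **That section 10.1.4 repeats the error or shows which figure is right.** It reports past exposure in other studies and sets no limit for this trial.
- **That SAP section 6.1 must change.** Its count of intravenous vials is a descriptive total of what was given and uses no maximum.
- **That a list of deviations must be rewritten.** The documents contain no such list with an infusion limit; deviations are classified at the Data Review Meeting.

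This review takes no position on which duration was intended.

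**What to change.** The sponsor should reconcile the day and hour figures in Protocol section 6.3 so that the sentence states one limit consistently. The natural place is the Phase 3 amendment required by SAP section 4.7; in any case the correction must be in force before any patient receives intravenous rescue. The Instructions to the Pharmacy, which are a separate document not available here, should be checked against the corrected text. Once section 6.3 has one limit, the Data Review Meeting can judge infusion length against it.

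The cost is one wording correction and one cross-check. No change to the design, sample size or analyses follows from it.
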